Study Design: The study is a 3-arm, randomized, double-blind, placebo-controlled, clinical trial. Patients will receive either 
 
i) oral GABA, dosed per kg, twice daily for 12 months plus 2 subcutaneous injections of 20 µg Diamyd in a prime-and-boost regimen over a period of 30 days
 
ii) oral GABA, dosed per kg, twice daily for 12 months, Placebo GAD-alum 2 subcutaneous injections over a period of 30 days.
 
iii) placebo.
 
 
The patients will be followed for a total of 12 months.

Selection of Subjects: Patients must be age 4 to 18years old, and diagnosed with Type 1 Diabetes (T1D) within the previous 5 weeks of randomization. Patients must be positive for GAD-65 autoantibody to be enrolled. They may, or may not be positive for the other autoantibodies at the time of enrollment, but all will be followed during the study.
Number of Subjects Planned: Approximately 110 patients will be enrolled.
Description of Treatment Groups: The patients will be assessed for eligibility prior to randomization. On Visit 1 (Day 1, baseline), patients eligible for the study will be randomized to 1 of 3 treatment groups: 
 
• 30 patients will be assigned to receive oral GABA twice daily, dosed per kg, from Day 1 through Month 12. In addition 2 subcutaneous injections with 20 µg Diamyd (GAD-alum) will be given at Day 1 and Month 1, i.e., 1 prime and 1 booster dose (providing a total dose of 40 µg Diamyd).
 
• 43 patients will be assigned to receive oral GABA twice daily, dosed per kg, from Day 1 through Month 12. In addition 2 subcutaneous injections with Placebo GAD-alum will be given at Day 1 and Month 1
 
• 37 patients will be assigned to receive oral Placebo GABA twice daily, dosed per kg, from Day 1 through Month 12. In addition 2 subcutaneous injection with Placebo GAD-alum will be given at Day 1 and Month 1
 

Name of Sponsor [name]
Name of Finished Product: GABA (Gamma-Aminobutyric Acid) DIAMYD® 20µg, subcutaneous injection (GAD-alum)
Name of Active Ingredient: Gamma-Aminobutyric Acid (GABA) Recombinant Human Glutamic Acid Decarboxylase (rhGAD65)

Primary Endpoint:
 
 
Evaluate the effect of GABA and GABA + GAD-alum combination on pancreatic beta cell function, as measured by meal stimulated C-peptide secretion levels compared to age-matched placebo controls, before and after one year of treatment.
 
 
Secondary Endpoints:
 
 
Evaluate the effect of GABA and GABA + GAD-alum combination on autoimmune diabetes autoantibodies: GAD-65, ICA512, and Zinc Transporter 8(ZnT8A) and the effect on HbA1c, fasting and stimulated glucose & glucagon levels, fasting C-peptide and the amount of daily insulin usage by participants, from baseline through subsequent visits
 
Evaluate the safety of GABA and GABA/GAD-alum combination
 
 
Safety The safety assessment includes observation of reactions at the injection site, occurrence of adverse events (AEs), laboratory measurements, neurological assessments, and limited physical examinations.
 
Sample size: The sample size for the proposed study is 110 children; 30 in the treatment group of active GABA and active GAD-alum, 43 in the treatment group receiving active GABA and placebo GAD-alum, and 37 in the placebo group. For the primary comparison of the 12-month post-baseline C-peptide measurements between these groups, assuming an <math>\alpha</math> of 0.05 and a mean (SD) C-peptide AUC of 1.0 (0.4) this sample size yields a ~97% power to detect a 50% difference. Adverse events and other data will be summarized descriptively.

### 3. Introduction and Rationale for Study

The primary defect in autoimmune Type 1 Diabetes Mellitus (T1DM) involves infiltration of the pancreatic islet cells by T-lymphocytes, macrophages, and other immune cells, and consequent loss of  $\beta$ -cells [1-3]. At the onset of T1DM, more than 70% of  $\beta$ -cells are destroyed [4], whereas the residual  $\beta$ -cells most likely represent the only reservoir for the potential regeneration of islet  $\beta$ -cell mass [5]. A series of immunological abnormalities have been reported in those with T1DM including, but not limited to, the production of autoantibodies (i.e., glutamic acid decarboxylase (GAD-65), tyrosine phosphatase-related islet antigen 2 (IA2), Zinc Transporter 8 (ZnT8A), or insulin (IAA)) as well as alterations in the capacity of regulatory T cells (Treg) to suppress the action of effector T cells (Teff); the latter population thought as playing a key role in the immune destructive processes. Therefore, a vast majority of studies attempting to prevent or reverse this disease have focused on immune suppression [6]. While these efforts have shown limited promise, most (including those investigated in children) have imparted multiple side effects which, in turn, have resulted in questioning the value for the short term benefits associated with utilizing these drugs [6-9]. Hence, the identification of agents with improved safety profiles, alongside the ability to preserve the metabolic capacity of  $\beta$ -cells, represents an important strategy. To that end, we hypothesize that gamma-aminobutyric acid (GABA), a naturally occurring substance in physiology, has the potential to locally reduce inflammation and protect pancreatic  $\beta$ -cells from auto-immune destruction.

GABA, synthesized from glutamate by GAD, is a well-known major neurotransmitter in the CNS [10] and acts mainly through the GABAA receptor (GABAAR) [11]. GABA is also locally produced by pancreatic  $\beta$ -cells [12]. GABAARs are also expressed in various immune cells, including T-cells, peripheral blood mononuclear cells, and are known to exert immune-inhibitory effects [13-15]. Interestingly, GABA appears to play multiple roles in the pancreas. Firstly, GABA promotes  $\beta$ -cell growth and survival [12]. Secondly, GABA can act on GABA(A) receptors in the pancreatic  $\alpha$ -cells, in so doing suppressing glucagon secretion [16]. Lastly, GABA suppresses inflammation and increases regulatory T-cell numbers [12]. In vitro assays determined that GABA suppressed the production of IL-12 by macrophages, and of IFN- $\gamma$  by CD8 T-cells concluding that GABA produces an anti-inflammatory effect by reducing the levels of these cytokines [12]. There are reports that in type 1 diabetic mouse models, GABA prevents and reverses the disease [12]. Soltani et al reported that mice with severe T1DM treated with GABA reduced lymphocytic islet infiltration, restored the  $\beta$ -cell mass and completely reversed hyperglycemia in these mice [12]. This was associated with increased serum insulin, decreased glucagon levels in the circulation, and improved glucose homeostasis.

#### *1.1 Significance (composed for layperson)*

As noted previously, T1DM is an autoimmune disease in which the body's immune system attacks and destroys the insulin producing  $\beta$ -cells of the pancreas. Therefore, the children affected by the condition present with high blood sugars. This condition is prevalent, affecting up to 1:400/500 persons worldwide. T1DM, previously known as juvenile diabetes, usually strikes in childhood, adolescence, or young adulthood, but lasts for a lifetime. To date, there have been no innocuous treatments that can arrest or reverse the ongoing  $\beta$ -cell destruction. Children with diabetes require multiple daily injections and, despite this, normal glucose regulation is exceedingly challenging. Moreover, they are at risk for heart disease, kidney failure, eye problems, and other complications from this life-long condition.

Based on the aforementioned information, we envisage that administering GABA to those with new onset T1DM may preserve or increase residual insulin production, suppress glucagon release, and decrease the inflammation surrounding the pancreas. With this, GABA may prolong the  $\beta$ -cell life after diagnosis. Combining with GAD-alum injections, which aim to halt the autoimmune attack by inducing tolerance thereby saving residual insulin production, may improve glycemic control even more and significantly decrease the risk of hypoglycemia and long-term complications in the future. There have been many other intervention trials for T1DM (including those involving children), but we believe this study has many clear advantages. First, GABA is widely considered safe and has very few side effects [17] and GAD-alum has been studied in approximately 700 patients in clinical trials with no safety concerns. In contrast, previously conducted studies of other interventions have typically involved some form of immunosuppression, which causes significant side effects that often outweigh the benefits [6-9]. Second, GABA is sold over-the-counter at many local food/health stores at a very reasonable cost (i.e., approximately \$5-7 per bottle) and GAD-alum is easy to use (subcutaneous injection twice over a 1 month period). If the hypothesis is substantiated, the economic and social impact would be profound as T1DM, besides its noxious effects, is an extremely costly disease to manage. Lastly, GABA is an oral treatment and GAD-alum only involves two subcutaneous injections in contrast to many other intervention trials in this subject population, which required multiple intravenous injections/infusions of medications, even to the point of those requiring extensive in-patient hospital days [18]. In sum, this pilot study may increase our current understanding of T1DM and may direct future therapies for new onset disease.

#### 4 Specific Aims

Conduct a randomized, double-blind, placebo controlled one year clinical trial utilizing GABA or GABA/GAD combination in patients with newly diagnosed T1DM.

##### 4.1 Objectives

- Evaluate the safety and influence of treatment with GABA on the preservation of residual insulin secretion in recent-onset type-1 diabetes.
- Evaluate the safety and influence of treatment with two doses of GAD-alum (Diamyd®) plus GABA on preservation of residual insulin secretion in recent-onset type-1 diabetes.

4.2 Primary Endpoint: Evaluate the effect of GABA or GABA/GAD combination administration on pancreatic beta cell function, as measured by meal stimulated C-peptide secretion levels compared to age-matched placebo controls, before and after one year of treatment.

##### 4.3 Secondary Endpoint:

- Determine the effect of oral GABA or GABA/GAD combination administration on autoimmune diabetes autoantibodies: GAD-65, ICA512, and Zinc Transporter 8(ZnT8A) and the effect it has on HbA1c, fasting and stimulated glucose and glucagon levels, fasting C-peptide the amount of daily insulin usage by participants from baseline through subsequent visits.
- Evaluate the safety of GABA and GABA/GAD –alum combination.

#### 5.0 Study Design

##### 5.1 Subject Recruitment:

The patients will be approached regarding the study at the time of admission for new onset T1DM at The Children's Hospital of Alabama, a tertiary care university referral care center with greater than 150 new -onset diabetics referred per year. Participants willing to enroll will be consented prior to discharge from the hospital, or at/before the one month hospital follow up visit. Approximately 110 patients, 4-18yrs of age, will be enrolled, 30 of which will be on both the oral(GABA) and injected( GAD-alum), 43 on oral GABA and 37 on placebo-see outline below. The endocrine research nurses will aide in identifying study candidates and contacting families to remind them of appointments. Both the PI and other faculty have been successful in recruiting subjects for clinical trials at this institution.

[figure not shown]
There will be 3 arms of the study:

- Placebo = all placebo, placebo oral GABA and placebo GAD-alum
- GABA = oral GABA plus placebo GAD-alum
- GABA and GAD-alum= oral GABA plus GAD-alum

##### 5.2 Study Outline

- 1) Males and females ages 4-18yrs will be recruited
- 2) Must meet ADA definition of Type I Diabetes
- 3) Must be positive for autoantibody GAD-65

## COHORTS

### 5.3 Inclusion Criteria

- Males and Females 4-18 years of age.
- Be positive for autoantibody GAD-65. If not collected. Collect and send at visit 1.
- They must meet the ADA criteria for diabetes : classic symptoms, plus blood sugar >200mg/dL or fasting blood sugar >126mg/dL
- Enrolled within 4 weeks of diagnosis (+ 1 week window)
- If the participant is female and post-menarchal two forms of contraception must be used during the study if not abstinent. The types of contraception deemed acceptable would be oral contraceptive pills, intrauterine devices and barrier methods.
- Signed informed consent form

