**Table 1. Randomization and study visits**

Study	Day 1 Baseline Randomization	Mo 1	Mo 5	Mo 8	Mo 12
	Visit 1 <5 weeks from diagnosis	Visit 2 ± 7	Visit 3 ± 7	Visit 4 ± 7	Visit 5 ± 7
Group 1 GABA-GAD group (GABA+GAD-alum)  30 subjects	GABA twice daily, every day from Baseline to Month 12				
	Prime injection GAD-alum 20 µg	Boost injection GAD-alum 20 µg			
Group 2  GABA group ( GABA+ Placebo GAD-alum)  43 subjects	GABA twice daily, every day from Baseline to Month 12				
	Prime injection Placebo GAD-alum	Boost injection Placebo GAD- alum			
Group 3  Placebo group (Placebo GABA + Placebo GAD-alum)  37 subjects	Placebo GABA twice daily, every day from Baseline to Month 12				
	Prime injection Placebo GAD-alum	Boost injection Placebo GAD- alum			

5.7 *Treatment Doses and Schedule*

- 1) Oral Gamma-Aminobutyric Acid (GABA)

We shall not exceed the recommended adult dosages (up to 1.5 grams/day) and we will adjust the dose to the body surface area of the children enrolled in our study. For example, the average adult has a body surface area of 1.5 - 2 m^2. Therefore, the current recommended adult dosage is equivalent to 1 grams/m^2/day, and this is the dose we will be giving to our trial participants. This total daily amount will be divided in two daily doses to be given with breakfast and dinner. The GABA will be supplied by the manufacturer NOW Foods in 200 mg capsules. Each dose will be rounded to the nearest 100 mg. The placebo will also be provided by NOW Foods and will be indistinguishable in appearance, taste, and smell from the GABA capsules. The capsules will be opened and dissolved in water, or sprinkled on food immediately before consumption. Documentation of these products by site personnel will be documented in the case report form (CRF).

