## 2) Subcutaneous GAD-alum

The Diamyd Drug Product (GAD-alum) is composed of the recombinant human GAD65 (rhGAD65) protein formulated in a sterile, non-pyrogenic phosphate buffered saline containing the aluminum hydroxide adjuvant, Alhydrogel, and will be provided by Diamyd Medical, Sweden (GAD-alum). The active ingredient, rhGAD65, is manufactured via a process involving expression in an insect cell line. The Drug product is supplied in a 3 mL glass vial with either 20µg Diamyd alum-formulated vaccine/mL or placebo. The dose volume is 0.5 mL for each subcutaneous administration. The vials have a slight overage to allow a withdrawal of 0.5mL. All dosing will take place in the hospital-based clinic, and handled only by trained, authorized study personnel.

All subjects will receive an injection of either GAD-alum or placebo at baseline (within 1 month after diagnosis), and a booster vaccine approximately 1 month later. The 20µg of GAD-alum (Diamyd Medical) is administered subcutaneously and, prior to exiting the clinic, the patient is observed for 1 hour post injection. The placebo injection has the equivalent components save, of course, the recombinant GAD, and is prepackaged in identical-appearing vials. The vials will be packaged into identical vial boxes. Both the vial box and the vial will be labeled with the same treatment number. Allocation of treatment to GAD-alum or placebo will be accomplished through Children's of Alabama Research Pharmacist.

The Diamyd Drug Product and Placebo Diamyd drug Product will be administered by the site personnel, and the administration will be documented in the site source documentation.

All vials of Diamyd and placebo will be kept between 2 and 8°C in a refrigerator that is behind a locked door in the Research Pharmacy to protect from unintended use. The temperature of the refrigerator is monitored constantly for accuracy. Any temperature deviations will be reported to Diamyd as soon as the site becomes aware of it. Vials should never be frozen, and any frozen vials should be rejected and is not allowed to be used clinically.

Diamyd product and placebo will be shipped from the distributor to the study site according to country specific laws and regulations. Diamyd product will not be offered to patients after the completion of the study. Participants will thereafter receive therapy at the discretion of the investigator.

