## 6 Visit Schedule, Study Procedures, and Laboratory Measurements

6.1 Our new-onset type 1 diabetic children are admitted to the hospital, typically at most for two days, for initial glucose management and diabetes education. Diabetes is defined per ADA recommendation [20]. All patients with newly diagnosed type 1 diabetes return for follow up at approximately one month after diagnosis. Prior to this visit subjects may be enrolled if consented and enrollment criteria is met. This will serve as the baseline visit. The second visit should then be scheduled one month from the baseline visit (second injection with GAD-alum/placebo) with a visit window of +/- 7 days. Please note that all visits must be calculated from the baseline visit according to the visit schedule. See table 2 for schedule of patients visits, visit windows and study drug administration.

If patients are febrile when scheduled for an injection, treatment will be postponed until the patient is afebrile.

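### Section 5.3 allows a missing GAD-65 sample to be sent at Visit 1, the day of randomization and first dosing, although the plan requires a positive result before enrolment

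*Combined protocol and SAP*

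**What the plan says.** The Synopsis (Selection of Subjects) makes the antibody a condition of entry: "Patients must be positive for GAD-65 autoantibody to be enrolled". Sections 5.2 and 5.3 repeat the requirement. The Synopsis (Description of Treatment Groups) also fixes the order of events: "The patients will be assessed for eligibility prior to randomization". Section 6.1 agrees, saying of the one-month follow-up visit: "Prior to this visit subjects may be enrolled if consented and enrollment criteria is met".

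The inclusion criterion in Section 5.3 then adds a fallback for a child without a sample: "If not collected. Collect and send at visit 1".

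Visit 1 is not a screening visit. The Synopsis says: "On Visit 1 (Day 1, baseline), patients eligible for the study will be randomized to 1 of 3 treatment groups". Table 1 labels the same column "Day 1 Baseline Randomization". Section 5.7 adds: "All subjects will receive an injection of either GAD-alum or placebo at baseline". Table 3 starts oral GABA or placebo at baseline too.

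The usual route is different. Section 6.7 and Table 3 have the antibodies drawn at diagnosis as standard of care, with those results used as baseline.

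**The concern.** A sample that is only sent on the day of randomization cannot show eligibility before randomization unless the result returns within that visit. If it does not, a child whose GAD-65 status is unknown is randomized and dosed. Should the result then be negative, the child has entered against the trial's own rule. A child in the combination arm would also have received GAD-alum, an investigational antigen intended here for GAD-65-positive children.

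The main stakes are exposure of an ineligible child and the clarity of the trial population. A secondary matter is how such a child is treated in the analysis, which the plan does not address specifically.

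**Working it through.** This is a question about the order of procedures, so the main check sets the sections side by side.

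1. **Entry rule.** GAD-65 positive, established before randomization (Synopsis; Sections 5.2, 5.3 and 6.1).
2. **Fallback.** Applies where no sample was collected; draw and send it at Visit 1 (Section 5.3).
3. **What else happens at Visit 1.** Randomization, first injection, start of oral dosing (Synopsis; Section 5.7; Tables 1, 2 and 3).
4. **Where the assay is run.** Section 6.7 sends antibodies to a named laboratory service, whereas the blood count and metabolic profile go to the hospital's own laboratories. No turnaround time is given.
5. **Any hold on randomization.** None found. Section 5.5 goes directly from consent to randomization. There is no separate screening visit, and the baseline antibody entry in Table 3 lists no Visit 1 draw.
6. **If the result is negative.** Section 6.6 lists three grounds for discontinuation: withdrawn consent, allergy and intolerable adverse event. Ineligibility found later is not among them, and nothing is said about the Month 1 injection. Section 9.0 makes intention to treat the basis of all analyses.

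Items 1 to 3 agree only if the result is back before randomization on the same day. Items 4 and 5 show that nothing secures this.

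**Size of the efficacy consequence.** Inputs from the Synopsis are two-sided alpha 0.05 (two-sidedness is my assumption), mean 1.0, SD 0.4, a 50% difference (0.5), and 30 combination versus 37 placebo children.

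- Standard error = 0.4 × √(1/30 + 1/37) = 0.4 × 0.2457 = 0.0983.
- Noncentrality with no ineligible children = 0.5 / 0.0983 = 5.09 on 65 degrees of freedom, giving power 99.9%.
- The plan states about 97%, which its literal inputs do not reproduce. With the 25 versus 35 of Section 10.0 they give 99.7% to 99.8%. That is a separate matter and does not bear on this point.

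Now suppose a share s of children is GAD-65 negative and has no treatment effect at all, so the difference becomes 0.5 × (1 − s). The documents give no value for s; these are assumptions.

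| s | Difference | Noncentrality | Power, 30 vs 37 (t-test) |
|---|---|---|---|
| 0 | 0.500 | 5.09 | 99.9% |
| 5% | 0.475 | 4.83 | 99.8% |
| 10% | 0.450 | 4.58 | 99.5% |
| 20% | 0.400 | 4.07 | 98.0% |
| 30% | 0.350 | 3.56 | 93.9% |

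This is harsher than the natural assumption that only GAD-alum is inert in negative children. Write the combination effect against placebo as a + g, with a from GABA and g from GAD-alum, taken as additive. A negative share s in that arm then gives a + g(1 − s). Only g shrinks by the fraction s; the whole arm effect shrinks by s × g/(a + g), which is less than s whenever a is positive. The GABA-only comparison (43 versus 37) does not change.

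**The case against.** The best defence is that the Synopsis and Section 6.1 already govern: a child who has not been shown to meet the criteria should not be randomized, and the fallback must be read subject to that. Testing at diagnosis is routine, so the sentence will seldom be used. It covers only children with no sample drawn. A child sampled at diagnosis with the result outstanding falls under the general rule.

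Most of this stands. It makes the case uncommon, and it makes the problem an internal contradiction rather than a deliberate choice to enrol children of unknown status. It does not remove the problem, because the general rule states a principle while Section 5.3 gives the site an operating instruction that can defeat it.

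A reader might infer four stronger things that the documents do not support.

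- **That a sizeable number of ineligible children will be enrolled.** No rate of uncollected samples, and no rate of negativity among them, is given.
- **That the result is certain to arrive after dosing.** This is a reasonable inference from sending the sample to a named laboratory service, but no turnaround time is stated. The remark in Section 6.7 that laboratory analyses are completed at the end of the study should not be stretched to cover an entry test normally done at diagnosis.
- **That the efficacy comparison is compromised.** The table above shows otherwise on the plan's own inputs.
- **That the analyst has no rule.** Section 9.0 supplies a default: a randomized child is analysed. What is missing is a specific statement for children later found negative.

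**Conclusion.** The contradiction is real and should be removed. Followed as written, Section 5.3 permits a child to be randomized and dosed before a required criterion is known, against the Synopsis and Section 6.1. Depending on allocation, a GAD-65-negative child could receive GAD-alum; 30 of the 110 planned children are in that arm.

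The frequency is unknown and should be low, given testing at diagnosis. The consequence is for eligibility, exposure and interpretation, and hardly for power. This rests on two things: the result not being available within Visit 1, which is inferred, and the absence of any hold on randomization, which is what the text shows.

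**What to change.** Reconcile Section 5.3 with the Synopsis and Section 6.1 by replacing the fallback sentence with wording such as:

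> If GAD-65 was not collected at diagnosis, collect and send it at or before consent and ahead of Visit 1. Randomize only when a positive result is on file, within the 5-week window. If consent falls at the one-month visit, schedule Visit 1 (baseline tests, randomization and dosing) after the result.

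The last sentence is needed because Section 5.1 allows consent as late as the one-month visit and Section 6.1 uses that visit as baseline, so the two can coincide. Section 5.7 places the first injection within one month of diagnosis, while Section 5.3 allows 4 weeks plus 1; the timing statements should be reconciled in the same amendment.

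Add to Section 9.0 that any child already randomized on a pending sample stays in the intention-to-treat and safety analyses. Add a sensitivity analysis restricted to children GAD-65 positive on a sample taken before the first dose, with status determined blind to arm. The sample must be pre-dose because Section 4.3 treats GAD-65 antibody as an outcome that treatment may change. The protocol should also say how later-found ineligibility is handled with respect to further study dosing, on which Section 6.6 is silent; that is for the sponsor and investigator to settle.

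The cost is a short amendment. A few children with late results may need an extra visit or may miss the 5-week window. Because families are approached during the initial admission, most missing samples can be sent well before the one-month visit.
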